Human Subjects Protocol

VA Puget Sound IRB

Do Rocker Bottom Shoes and Ankle-Foot Orthoses Reduce Pain and Improve Mobility for Ankle Osteoarthritis Patients?

MIRB # 01601

Funding Agency: Department of Veterans Affairs

Principal Investigator: [name]

Version 10; 01/10/2022

Abstract

Background and Purpose: Ankle osteoarthritis (OA) is a painful, progressive condition that can severely limit physical activity and reduce quality of life. **Rocker bottom (RB)** shoes and **ankle-foot orthoses (AFO;** a type of ankle brace), are common non-surgical treatments to manage ankle OA, but their ability to reduce pain and increase mobility has not been fully evaluated. One way ankle OA pain can be managed is by reducing the ankle's **range of motion (ROM)**, the less the joint has to move during activities (like walking) the less load it has to carry/process. RB shoes have curved soles, front-to-back, that may alleviate joint pain by reducing the ankle's front-to-back ROM. RB shoes may allow the body's weight to rollover the curved sole of the shoe during activities (like walking) with less effort and movement needed from the ankle joint. Similarly, AFOs may reduce joint motion by securing the foot and ankle within the AFO structure.

The purpose of this study is to evaluate the ability of RB shoes and AFOs to improve mobility, by alleviating pain and reducing joint motion when compared to a standard shoe. This study has three specific aims (SA):

SA 1: Compare the daily step count, **self-selected walking speed (SSWS)**, and self-reported outcomes from a set of questionnaires assessing pain and mobility before and after wearing a control shoe, RB shoe and a AFO. Each footwear condition will be worn over a three-week period (one-week acclimation, two-week trial period). This will indicate how subjects respond to these treatment conditions – what their pain levels are compared to baseline, how they self-report functional change, and from their step count, a quantitative measure of their mobility in the treatment footwear.

SA 2: Evaluate the effect of a control shoe, a RB shoe and a AFO on the front-to-back ROM of the foot and ankle. This will determine how these devices shield the ankle from motion – potentially protecting it, and if they impose abnormal motion on adjacent foot joints – potentially exposing them to additional wear and increasing their risk for long term OA development.

SA 3: Compare the ankle OA clinical and biomechanical outcome measures for the control shoe, RB shoe, and AFO to a healthy control group wearing control shoes. This will determine the difference in clinical and biomechanical outcomes related to the presence of OA.

Methods: We will enroll 100 participants with ankle OA and 50 control participants without lower limb pain. Three study groups will participate in this project. Study group 1 is a single day study and have images taken using our biplane fluoroscopy system. Study group 2 is a three month take home, and Study group 3 is a three month take home and will have images taken using our biplane fluoroscopy system. At visit-1 all participants will do baseline measures (questionnaires and functional assessments, including **SSWS**) and have a CT scan. During the initial visit, group 1 will participate in a biplane assessment. Participants in Study group 2 & 3 will be assigned to a randomly selected order of footwear (RB shoe, control shoe or an AFO). Each footwear condition will be worn for a three-week trial period at-home/in-community (one-week acclimation, two-weeks continuous wear). Participants will complete brief weekly pain assessments and wear a step counter. At visit-2 participants will do a pain rating, repeat the questionnaires and SSWS test, and group 3 will have images taken using our biplane fluoroscopy system. Participants will continue wearing the step-counter during a one week washout period. For the next three weeks, participants will repeat the at-

home/in-community procedures (step counter, weekly pain rating) and come to the VA to repeat the visit-2 procedures. The same process will be repeated for the third footwear condition.

List of Abbreviations

Provide a list of all abbreviations used in the protocol and their associated meanings.

AE - adverse event

AFO - ankle-foot orthosis

CT - computed tomography

mSv - millisievert

OA - osteoarthritis

RB - rocker bottom

ROM - range of motion

ROP - report of other problem

SAE - serious adverse event

SSWS - self-selected walking speed

UW/HMC - University of Washington/Harborview Medical Center

Contents

Protocol Title: Do Rocker Bottom Shoes and Ankle-Foot Orthoses Reduce Pain and Improve Mobility for Ankle Osteoarthritis Patients?..... 6

1.0 Key Study Personnel..... 6

2.0 Introduction..... 6

3.0 Specific Aims and Hypotheses..... 7

4.0 Resources and Personnel..... 8

5.0 Study Procedures..... 8

 5.1 Study Design..... 8

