We will take video and photos of participants during portions of this study for documentation and use in research publications. All videos and photos will be anonymized (to avoid facial or voice identification) and tattoos and other distinguishing marks will be covered before images are captured or obscured during processing to protect the identity and privacy of our participants.

During study sessions, visitors and observers will not be allowed in the lab unless the participant agrees to their presence; the participant can change her/his mind at any time.

Study Footwear

Over the course of the study (one day or ~3 months) participants will be asked to wear up to three different footwear conditions: control shoes (a typical walking shoe, such as the New Balance 928), RB shoes (walking shoes with a front-to-back curved sole, such as the New Balance 928 with a rocker sole), and an orthotic device (such as an AFO, an ankle brace, such as the Toeoff[®] AFO) with control shoes. Participants will wear each footwear condition, in a randomized order. For all footwear conditions a fitbit zip may be clipped or taped to the shoe. This will record steps taken in the footwear. The fitbit will be synced during the VA visits and will only record number of steps. A separate account for each fitbit will be created and the account number will be recorded on the participant crosswalk. There will be no additional methods to link the data to the participant. Additional assessments on the initial day may include barefoot and own shoe as footwear conditions.

Screening /Eligibility Verification

Participants will have been preliminarily screened during recruitment, then during the first visit, after informed consent, we will make a final eligibility determination. This will include verifying that the information collected during recruitment is accurate and current.

If a participant cannot continue in the study, they will be compensated \$50 for the visit.

Demographic Data collection

Participants' age, sex, race/ethnicity and Veteran status will be recorded.

Anthropometrics

Participants' weight, waist circumference, and height will be measured.

Pain/health screening

Short survey which will include questions regarding trauma history in the lower limbs, joint replacements, OA, and pain throughout the body.

Functional Assessments

Self-selected Walking Speed (SSWS)

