Over the course of the study, participants with ankle OA will repeat the biplane fluoroscopy session 3 times (once for each footwear condition). Participants in study group 1 will complete the biplane in one session while barefoot, or wearing their own shoes, the control shoes, RB shoes, and/or the AFO. Each participant will receive no more than 80 total biplane imaging trials as part of the study.

Participants enrolled in study group 3 will continue wearing the StepWatch. Those in study group 1 have completed their participation and will return the study footwear and StepWatch.

Take home study

Length of participation

For participants with ankle OA, study procedures will occur over ~3 months (11 weeks). Four study visits will be done at the VA Puget Sound where three at-home/in-community study footwear (control shoes, RB shoes, an AFO) condition periods will be conducted.

Visits at the VA Puget Sound may last up to 4 hours each. Participant schedules and the accessibility of facility resources may extend the study timeframe beyond these estimates. Study visits will be scheduled by contacting the participants on phone, or during in-person contacts. We may contact participants with appointment and/or at home activity reminders via email or phone.

Assessment 1

During this initial assessment participants will complete the, Screening, Functional assessments, LineUP with pregnancy test (not Study group 4), Questionnaires, and Brief Pain Rating. Participants will be given a StepWatch and the first footwear condition. At the first assessment, participants who elect to use Ilumivu will be assigned a randomized username for the ilumivu mobile application. The link between this unique ID and the Veteran's identity will not be stored in the mobile application, but rather, stored locally at the Seattle VA. Further information about data security can be found in the Data Security section of this application. Ilumivu, is an app downloaded onto your phone. This app and its developers do not have any information that can be linked back to the participant. Only the researchers will know the Ilumivu participant ID. The Ilumivu participant ID will be recorded on the participant crosswalk in the research folder on the R drive. There will be no additional methods to link the data to the participant.

In Home/Community - Footwear Condition 1: Acclimation and Continuous Wear Period (3 weeks)

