This process establishes a tibial anatomical coordinate system and a talar coordinate system for measuring talocrural joint ROM. These same methods will be used to measure talonavicular, naviculocuneiform, and the first cuneometatarsal kinematics. By performing this template matching algorithmically, we can ensure consistency in post processing of anatomical coordinate systems between subjects.

Statistical Methods:

For **Specific Aim 1**, linear mixed effects regression will be carried out to test for differences in mean step count, self-selected walking speed, physical function or pain (the dependent variables) by intervention, (control shoe vs. RB shoe vs. AFO, the independent fixed effect) with study subject as a random effect. If the omnibus test for the association between outcome variables and intervention is significant, pairwise comparisons will be carried out to assess differences in mean outcomes between the RB shoe or the AFO and the control shoe (Hypothesis 1.1) and between the RB shoe and the AFO (Hypothesis 1.2).

For **Specific Aim 2**, linear mixed effects regression will be used as above to examine differences in mean [sagittal plane] ROM (the dependent variable) by intervention (control shoe, RB shoe, AFO; the independent fixed effect) with subject and subject by intervention interaction as random effects. If the omnibus test for association between [sagittal plane] ROM and foot intervention is significant, pairwise comparisons will be carried out to assess differences in mean [sagittal plane] ROM between the RB shoe, the AFO, and the control shoe (Hypothesis 2.1). Secondary analyses will be carried out using methods similar to those described above to determine if the interventions affect frontal and transverse plane joint ROM.

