Ten thousand datasets were generated using mean [sagittal] ROM for the control foot of 15.3 degrees, between subject SD of 2.0 degrees, and within subject SD of 2.4 degrees.⁸⁴ Power was estimated for sample sizes of 15 and 20 subjects and for a 1.5 degrees and 2.0 degrees difference in [sagittal] ROM between the control shoe and the RB shoe or AFO. Hypothesis testing for each bootstrapped sample for the reduction in ROM was carried out using a linear mixed effects regression of [sagittal] ROM (the dependent variable) on foot (ROM or AFO vs. control) with study subject and subject by intervention interaction as random effects. Power was estimated by determining the number of tests that were significant at the 0.05 level using the likelihood ratio test. The analysis indicated that if the footwear induces a 1.5 degrees change in ankle [sagittal] ROM then a sample size of 20 or 15 subjects results in 94% or 84% power, respectively. If the change in ROM is 2.0 degrees, then even with only 15 subjects the study has 98% power (Table 2). Note that we expect the change in [sagittal] ROM to be significantly more than 1.5 degrees but even for this small difference our study is adequately powered with 25 subjects. Based on these results, we plan to enroll 30 subjects into the

study and expect several to drop out leaving a sample size of at least 25 subjects and the study power greater than 94% (Table 2).

Simulated [sagittal] ROM difference between the control shoe and RB shoe or AFO	Number of subjects	Estimate power
1.5 degrees	15	84%
2.0 degrees	15	98%
1.5 degrees	20	94%

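### The plan does not require footwear order to be balanced over the six possible orders, and the Aim 1 and Aim 2 models have no period term: a modest loss of precision, not a bias

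*Combined protocol and SAP*

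**What the plan says.** The design is a three-period crossover: "three at-home/in-community study footwear (control shoes, RB shoes, an AFO) condition periods will be conducted" (Section 5.5, Length of participation), with one-week washouts between conditions.

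Two places describe allocation. The Abstract (Methods) says "Participants in Study group 2 & 3 will be assigned to a randomly selected order of footwear (RB shoe, control shoe or an AFO"). Section 5.5 (Study Footwear) says "Participants will wear each footwear condition, in a randomized order". The documents mention no list, blocks, Latin square, stratification or concealment for the order. The sentence in the Abstract names groups 2 and 3 only, although Section 5.5 also describes a remote take-home group 4.

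Section 5.6 (Statistical Methods) models the Aim 1 outcomes "by intervention, (control shoe vs. RB shoe vs. AFO, the independent fixed effect) with study subject as a random effect". Aim 2 uses the same fixed effect "with subject and subject by intervention interaction as random effects". Neither model has a period or sequence term.

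**The concern.** Three conditions can be worn in 3! = 6 orders. If each participant's order is drawn without restriction, the numbers per order will differ, so one footwear will fall more often in an early or late period than another. Step count, pain and walking speed could drift over about 11 weeks through season, novelty or repeated testing. With no period term, that drift enters the estimated footwear differences of the trial as run, to the extent that footwear and period are unequal. Balance by design or adjustment in the model would each limit this, and the plan specifies neither. What is at stake is precision, mainly if the analysed number is small.

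**Working it through.** **The plan's own figures.** No stated figure concerns allocation of order. The nearest is the power simulation in Section 5.6, with "between subject SD of 2.0 degrees, and within subject SD of 2.4 degrees". With one observation per condition, the SE of a contrast at n = 15 is 2.4 × √(2/15) = 0.876 degrees, and power for 1.5 degrees is Φ(1.5/0.876 − 1.96) = 40%, against 84% stated. Assuming three trials per condition and no subject-by-intervention variance, the SE is 2.4 × √(2/45) = 0.506. The normal approximation then gives 84.2%, 97.7% and 92.8%, against 84%, 98% and 94% stated. The number of trials is not given, so this match is conditional. It serves only to scale the results below.

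**Inputs.** Six orders, each with probability 1/6 (an assumption: unrestricted draws). n = 25 to 30 comes from the Power Analysis, which enrols 30 and expects at least 25 to remain. n = 100 is the ankle OA total in the Abstract. The split over study groups is not stated, so 100 is an upper limit for the take-home groups.

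**Step 1: imbalance.** For one participant, the difference in period number between two footwear conditions is ±1 with probability 2/3 and ±2 with probability 1/3. Its mean is 0 and its variance is (2/3)(1) + (1/3)(4) = 2. The mean difference over n participants therefore has expectation 0 and SD √(2/n):
- n = 25: 0.28
- n = 30: 0.26
- n = 100: 0.14

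A simulation of 20,000 allocations gave the same values. At n = 30, the chance of exactly five participants on every order is 30!/((5!)^6 × 6^30) = 0.0004.

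**Step 2: effect without a period term.** For a linear drift of d per period, the chance shift in a contrast has SD d√(2/n). For an assumed drift of 0.5 to 1.0 degree per period, that is 0.13 to 0.26 degrees at n = 30 and 0.07 to 0.14 at n = 100. The smaller effect in the power section is 1.5 degrees.

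**Step 3: effect with a period term.** With subject and period as fixed effects, 1,500 simulated allocations per n gave this variance of the AFO–control contrast relative to full balance (2σ²/n, with σ the residual SD):
- n = 25: mean 1.044, 95th percentile 1.137
- n = 30: mean 1.036, 95th percentile 1.107
- n = 100: mean 1.011, 95th percentile 1.031

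**Step 4: are the planned tests valid?** A drift of −d, 0, +d adds 2d² to each participant's within-subject sum of squares on 2 degrees of freedom, so the residual variance becomes about σ² + d². The model's SE² is then 2(σ² + d²)/n. Under unrestricted draws the true variance is 2σ²/n + 2d²/n, which is the same, so type I error stays near 5%.

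**Step 5: blocking without a period term.** In a balanced allocation the true variance falls to 2σ²/n, but the model still reports 2(σ² + d²)/n. Type I error is about 2Φ(−1.96√(1 + d²/σ²)). That is 2.8% at d = 0.5σ and 0.6% at d = σ; simulation at n = 30 gave 3% and 0.5%. The tests become conservative, and the benefit of balance does not reach the reported standard errors.

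**Step 6: what blocking achieves.** With blocks of six, n = 30 can be exactly balanced (SD 0). At n = 25, four full blocks plus one participant leave an SD of √2/25 = 0.06, against 0.28.

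**The case against.** The strongest objection is that the documents do not describe an unbalanced scheme. A reader might infer that order is drawn ad hoc for each participant instead of being balanced. The wording does not support that: a concealed, blocked list of the six orders would also fit it. This stands. The documented gap is an unspecified method, and the figures above apply only if draws are unrestricted.

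A reader might also infer that drift biases the footwear comparison. It does not: the expected shift is zero, and the planned standard errors already reflect the chance component on average (Step 4). This also stands.

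It can further be said that the missing period term matters more than the allocation. That is fair. With period in the model, unrestricted draws cost only about 4% at n = 25 to 30 and 1% at n = 100. Without it, a drift of half a residual SD adds 25% to the contrast variance (1 + 0.5² = 1.25). Blocking is therefore worth little unless period is added as well.

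Finally, perfect balance is not attainable in practice. n = 25 is not a multiple of six, the Power Analysis expects dropouts, and Section 5.5 allows a participant to move on from a footwear that does not fit. This limits the gain but does not remove it.

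**Conclusion.** The concern holds as a minor one. The protocol neither states how footwear order is generated nor requires balance over the six orders, and the Aim 1 and Aim 2 models omit period. If draws are unrestricted, the cost at n = 25 to 30 is about 4% of contrast variance on average with period adjusted for. Without adjustment it is a chance shift with an SD of about 0.26 to 0.28 of one period's drift. At n = 100 these fall to about 1% and 0.14.

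The figures rest on equal-probability independent draws, complete data, and linear drift for the unadjusted case. The documents give no size for the drift, so the shift is best read as a multiple of it. The Power Analysis does not say that its 25 to 30 participants are the imaged group, so the figures for that range should not be read as a statement about group 3 alone.

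**What to change.** 1. State the allocation method in Section 5.5: the six orders in permuted blocks of mixed size 6 and 12, from a list prepared in advance and concealed from enrolling staff, separately for take-home groups 2, 3 and 4. Name group 4 in the allocation text.
2. Add period as a three-level fixed effect to the Aim 1 and Aim 2 models in Section 5.6. Aim 3 reuses these models with a healthy-control category, so state how period is coded for participants outside the crossover.

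The cost is small. No visit, device or sample size changes. The last order in a block may be guessed; mixed block sizes limit this, and every participant is due to receive all three conditions. Period uses two degrees of freedom: with 30 complete participants, the within-subject residual falls from 58 (60 − 2 for footwear) to 56.

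Some imbalance will remain from incomplete blocks in each group, dropouts and skipped conditions. Balance also does not remove carryover. No footwear follows itself, so with six equal orders an unadjusted contrast of A with B still contains one third of the carryover of B minus that of A. Protection against this still rests on the one-week washout.

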2.0 Introduction

Ankle osteoarthritis (OA) is a debilitating condition associated with severe pain, dysfunction, and reduced quality of life. In the end stage of the disease, many patients are unable to walk 100 meters or up a single flight of stairs¹, and the reduction in quality of life is similar to that of end-stage hip arthritis or congestive heart failure^{1,2}. Ankle OA affects about 6% of the population³ and is thus less common than hip or knee arthritis. However, ankle OA differs from hip or knee arthritis because most cases are post-traumatic² and consequently affect a younger demographic^{4,5}. Data from the Health Care Utilization Project online indicate that hospital charges for the treatment of ankle arthritis exceed \$370 million per year.

Ankle OA is an important health care concern for the Veterans Health Administration. Veterans are at greater risk of developing ankle OA than non-veterans due to the rigorous physical demands associated with training and combat during military service⁶. Traumatic OA from injury is also higher in the military population (up to seven times greater⁷). Data from the National Health Interview Survey of 1990 show a higher prevalence of foot and ankle OA among veterans of the pre- Gulf War era than corresponding non-veterans⁸, and studies of Operation Enduring Freedom/Operation Iraqi Freedom (OEF/OIF) have shown both an increase in extremity injury and an increase in ankle OA compared to previous conflicts^{9,10}. This increase in ankle OA has resulted in severe disability for many veterans. A recent study of 126 wounded warriors with OA as an unfitting condition that led to a medical separation from the military, found that those with ankle OA had higher disability ratings than those with knee or hip OA¹¹. VA Medical Centers treat a significant number of veterans with ankle OA. A VHA Support Service Center (VSSC) database search for FY2014 of local (Seattle VA), VISN 20, and national outpatients yielded the following table of ankle OA populations, showing several thousand national cases in a single year.

End-stage ankle OA is defined as when all non-surgical treatment options (nonsteroidal anti-inflammatory drug therapy, other oral therapy, corticosteroid injections, bracing, etc.) for ankle OA have failed. The most common surgical treatments are talocrural arthrodesis and total joint arthroplasty. However, the long-term results are mixed, with most ankle arthrodesis patients developing arthritis of the subtalar or midfoot joints within 3-22 years of operation^{12,13} and many ankle arthroplasty patients have a higher failure rate than the knee or hip¹⁴. These late effects suggest

that a longer delay in surgical treatment is desirable. Yet there are very few publications on efficacy of orthotic management.

The risks, the cost, and the time-limited outcomes are compelling reasons to explore non-surgical treatments options for ankle OA. Conservative interventions thought to limit joint range of motion (ROM) may delay or prevent the progression of arthritis, reduce pain, improve comfort and function, and thus improve quality of life. Two such treatment types are rocker bottom (RB) shoes and ankle-foot orthoses (AFOs). These devices are commonly prescribed to manage ankle OA; however, their ability to reduce joint motion and thus alleviate pain and increase mobility has not been scientifically evaluated. Towards that end, we aim to compare two conservative treatments (RB shoes and AFOs) in OA subjects by measuring mobility and pain during and after the completion of three-week trial periods. We will use biplane fluoroscopy to measure hindfoot and midfoot joint motion at the conclusion of each period. This study will provide evidence to support clinical decision making.

